^j Disease assessment will be performed on blood, bone marrow samples, and/or other tissue samples at these time-points. For Group 1 and Group 2, the screening disease assessment may be performed as part of SoC (prior to consent if it was already completed). For Group 1, pre-transplant testing of MRD should be performed locally by any testing methodology and results recorded in the eCRF. Post-transplant baseline MRD testing will be performed centrally, and results must be available prior to randomization. If any additional disease assessments, such as additional time points or additional testing (e.g., imaging for extramedullary disease), or visits occur due to clinical necessity, information will be recorded on eCRF. Includes central testing for MRD status for all samples collected as per SoC and as per standard institutional guidelines at other time points by methods outlined in protocol in Section 4.1 (samples stored for central confirmation at later date). If imaging is performed on a patient, the Sponsor may request imaging to be sent to a central vendor along with any disease assessment reports.

Disease assessment at Day 0 for Group 1 only (disease assessment does not need to be repeated if within 3 weeks of prior disease assessment and results can be pending prior to treatment).

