Study treatment is administered for all patients (except SoC - Group 1- Arm B) on Day 0 and every 2 weeks for a planned maximum of 3 doses. Patients randomized to SoC (Group 1B) at 80 days post-transplant may crossover to the relapse group (Group 2) if the patient is found to have relapse of disease (MRD* or frank relapse) and the subgroup is open and/or Sponsor agreement. After relapse and prior to bridging chemotherapy, the patient should perform assessments associated with the Screening visit if not already completed. The patient should perform the assessments associated with Baseline following bridging chemotherapy and prior to MT-401 administration. The patient will have their visits reset and have their MT-401 administered on Day 0 and follow the schedule of events from that point forward. Group 1- Arm B (SoC) patients will continue to follow the SoA minus administration of MT-401. Refer to Section 6 for additional dosing details. Administration of MT-401 can be delayed due to management of AEs or other toxicities, but patients should resume T cell infusions within 2 weeks of their scheduled dose. If greater than 2 weeks is needed, Sponsor will determine if patient can resume T cells infusions.

m All AEs and SAEs, from Day 0 and Baseline, respectively, to the Week 12 Visit will be collected; after Week 12, only treatment-related AEs and SAEs will be collected.

ⁿ Detailed studies outlined in Section 8.8.

o Additional details regarding the PRO questionnaire and associated instructions will be provided in a separate document.

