9.3.1. Primary Safety Analysis: Safety Lead-In (Cohorts I and II) and Cohort III-V

The primary objectives for the Safety Lead-in are to assess safety and tolerability of MT-401 manufactured using peptides produced by two different vendors, including identifying DLTs. The primary objective for Cohort III is to assess the safety and tolerability of a higher dose than the dose used in the Phase 2 portion of the study. The primary objective for Cohorts IV-V is to assess the safety and tolerability of the accelerated MT-401 product. For both the Safety Lead-in, which includes Cohorts I and II, and Cohorts III-V, the number of DLTs per cohort will be identified as defined in Section 5.6. The confirmed dose and peptide manufacturer will be identified based on the procedures of the standard 3+3 design described in Section 4.5 and review of entirety of the safety data. Safety endpoints will be analyzed as discussed in Section 9.3.5.

9.3.2. Primary Efficacy Analysis: Group 1

The primary endpoint for Group 1 is RFS, defined as the time between the date of randomization and the date of first relapse per ELN recommendations or death by any cause, whichever occurs first. For patients who remain alive and whose disease has not relapsed, RFS will be censored on the date of last evaluable disease assessment. For patients who remain alive and have no recorded post-randomization disease assessment, RFS will be censored on the date of randomization. Censoring rules for the primary analysis of RFS in Group 1 are presented in Table 9.

Relapse includes either hematologic and/or molecular relapse as defined in Table 6 at any disease assessment.

Confidential Page 52 of 74

For the interim analysis, RFS as determined by the investigator will be used.

Table 9: Censoring Scheme for Primary definition of RFS

Situation	Date of Event or Censoring	Outcome
Relapse per ELN recommendations	Date of first relapse	Event
Death without relapse	Date of death	Event
No baseline disease assessment	Date of randomization	Censored
No on-study disease a ssessments and no death	Date of randomization	Censored
No relapse and no death	Date of last evaluable disease	Censored
	assessment	
New anti-cancer therapy received without relapse	Date of last evaluable disease	Censored
reported prior to or on the same day as disease	assessment on or prior to the date of	
assessment	initiation of subsequent therapy	
Two or more consecutive missed scheduled disease	Date of last evaluable disease	Censored

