complete response is defined as the time between the date of first documented response of CR_{MRD} - to the date of the first documented relapse per ELN recommendations or death due to any cause, whichever occurs first.

The CR rate from Group 2 Subgroup C will be evaluated in the context of results from an ongoing retrospective study of AML patients who are similar to the inclusion/exclusion criteria of Group 2 Subgroup C patients. Any comparison of Group 2 data to results from the retrospective study will be described in a separate SAP.

Censoring rules for DOCR are provided in Table 10.

Table 10: Censoring Scheme for Primary Definition of DOCR

Situation	Date of Event or Censoring	Outcome
Relapse per ELN recommendations	Date of first relapse	Event
Death without relapse	Date of death	Event
No relapse and no death	Date of last evaluable disease assessment	Censored
New anti-cancer therapy received without relapse reported prior to or on the same day as disease assessment	Date of last evaluable disease assessment on or prior to the date of initiation of subsequent therapy	Censored
Two or more consecutive missed scheduled disease assessments	Date of last evaluable disease assessment prior to the missed disease assessments	Censored

Abbreviations: AML=acute myeloid leukemia; RFS=relapse-free survival

Relapse includes either hematologic and/or molecular relapse as defined in Table 6 at any disease assessment.

The CR rate and the corresponding 95% exact CI will be calculated. The DOCR will be estimated using the KM product limit method. The KM estimate of the median DOCR and the DOCR rates at milestone timepoints will be reported along with the two-sided 95% CI.

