6.4.1.2 Primary Efficacy Variables

Phase 2 Adjuvant (Group 1):

- RFS: defined as the time between the date of randomization and the date of first relapse per ELN recommendations or death by any cause, whichever occurs first. Relapse includes either hematologic and/or molecular relapse as defined in [Table 2](#) at any disease assessment. In the event that no relapse or death is documented prior to analysis cutoff or the start of new anti-cancer therapy, RFS will be censored on the date of the last evaluable disease assessment demonstrating no relapse prior to analysis cutoff or the start of new therapy. For patients who remain alive and have no baseline disease assessment or have no post-randomization disease assessment, RFS will be censored on the date of randomization. In addition, if relapse or death occurs after extended time without disease assessments, RFS will be censored on the date of the last evaluable disease assessment prior to the missed disease assessments.

For patients with relapse or death, a variable will be created to flag whether the earlier date of relapse or death occurs after extended time without disease assessments. The extended time is defined as below:

- Time from randomization date to Day 0 visit + 12 weeks + assessment window of 2 weeks, if the latest assessment prior to the event (relapse or death, whichever is earlier) \leq randomization date + 0.5*time from randomization date to Day 0 visit. For patients without Day 0 visit, an artificial Day 0 visit will be derived as randomization date + mean time from randomization date to Day 0 visit date in MT-401 arm, for analysis purpose only.
- 24 weeks + assessment window of 2 weeks, if the latest assessment prior to the event (relapse or death, whichever is earlier) \leq Day 0 visit + 6 weeks & $>$ randomization date + 0.5*time from randomization date to Day 0 visit
- 38 weeks + assessment window of 5 weeks, if the latest assessment prior to the event (relapse or death, whichever is earlier) \leq Day 0 visit + 18 weeks & $>$ Day 0 visit + 6 weeks
- 78 weeks + assessment window of 5 weeks, if the latest assessment prior to the event (relapse or death, whichever is earlier) \leq Day 0 visit + 37 weeks & $>$ Day 0 visit + 18 weeks
- 104 weeks + assessment window of 5 weeks, if the latest assessment prior to the event (relapse or death, whichever is earlier) \leq Day 0 visit + 78 weeks & $>$ Day 0 visit + 37 weeks

Phase 2 Active Disease (Group 2):

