- CR: For Subgroup C, CR is defined as the proportion of patients who achieve a best response of CR_{MRD-} or CR using the ELN recommendations. For Subgroup D, CR rate is defined as the proportion of treated patients who achieve a best response of CR_{MRD-}. Best overall response (BOR) is defined as the best response designation recorded between the date of first dose and the date of objectively documented relapse per ELN recommendations or the date of subsequent therapy, whichever occurs first. For patients without documented relapse or subsequent therapy, all available response designations will contribute to the BOR assessment.
 - The incidence of converting MRD+ to MRD- was chosen as the primary endpoint for Subgroup D based on the following rational: (1) 2017 ELN recommendations (Döhner et al, 2017) introduced a new response category of CR MRD- recognizing MRD assessment provides a more reliable predictor of outcome than morphological assessment and MRD status has been consistently shown to be an independent prognostic marker for disease outcome (Short et al, 2020; Schuurhuis et al, 2018). (2) Given the nature of single arm design, a binary endpoint was considered a more appropriate primary endpoint than a time to event endpoint such as RFS or OS.
- DOCR: For Subgroup C, DOCR is defined as the time between the date of first documented response of CR_{MRD-} or CR to the date of the first documented relapse per ELN recommendations or death due to any cause, whichever occurs first. For Group 2 Subgroup D, duration of complete response is defined as the time between the date of first documented response of CR_{MRD-} to the date of the first documented relapse per ELN recommendations or death due to any cause, whichever occurs first. For patients who neither relapse nor die prior to analysis cutoff or the start of new anti-cancer therapy, DOCR will be censored on the date of their last evaluable disease assessment on or after the assessment of first documented CR and prior to analysis cutoff or start of new therapy.

6.4.1.3 *Secondary Efficacy Variables*

Safety Lead-in (Cohorts I and II) and Cohorts III-V:

- CR (Active disease patients): defined as above for Group 2
- DOCR (Active disease patients): defined as above for Group 2

Phase 2 Adjuvant (Group 1):

- OS: defined as the time between the date of randomization and the date of death. A patient who has not died will be censored on their last contact date (“last known alive date”).

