7.7 Changes in the Conduct of the Study or Planned Analyses

There were no changes to the study conduct or planned analyses identified within the development of this SAP, relative to the descriptions provided within the clinical study protocol.

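### The SAP uses only assessments before new anti-cancer therapy starts, while the protocol's censoring tables also use one made on the day it starts; the SAP declares no change

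*SAP*

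**What the plan says.** **SAP 6.4.1.2, RFS.** The event test is strict: if "no relapse or death is documented prior to analysis cutoff or the start of new anti-cancer therapy, RFS will be censored". The censoring date is strict too, being the "last evaluable disease assessment demonstrating no relapse prior to analysis cutoff or the start of new therapy".

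**SAP 6.4.1.2, duration of complete remission (DOCR).** The pattern is the same: "For patients who neither relapse nor die prior to analysis cutoff or the start of new anti-cancer therapy, DOCR will be censored". SAP 6.4.1.3 uses equivalent wording for GRFS, DOR and PFS. The SAP has no censoring table.

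**Protocol 9.3.2, Table 9 (RFS).** One row makes relapse an event at the date of first relapse, with no condition attached. Another row covers new anti-cancer therapy received without a relapse "reported prior to or on the same day as disease" assessment.

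**Protocol censoring date for that row.** Table 10 (DOCR) prints it without a line break: "Date of last evaluable disease assessment on or prior to the date of initiation of subsequent therapy". Tables 9, 11 (GRFS) and 12 (PFS) say the same. DOR has no table of its own; Protocol 9.3.4.3 appears to send it to the DOCR methods.

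**SAP 7.7.** "There were no changes to the study conduct or planned analyses identified within the development of this SAP". SAP section 4 undertakes to explain any change in method from the protocol.

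**The concern.** Dates are normally recorded to the day, so an assessment and the start of new therapy can share a date. A programmer working from the SAP would code a strict inequality and discard that assessment. A patient who relapses and is treated the same day would then enter the primary analysis as censored and relapse-free. The reason for censoring would be the relapse itself, so the censoring is informative.

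The trial is open-label and RFS is its randomized primary endpoint. The Group 1 interim analysis in SAP 7.4.7.3 takes place at 45 events, with hazard-ratio and conditional-power thresholds. Each reclassified event there is 1/45 = 2.2% of the event count. The tie rule should therefore be settled before anyone sees data by arm.

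**Working it through.** **1. The two rules for one patient.** Suppose an assessment and the start of new therapy fall on the same date.

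| Same-day finding | Protocol Tables 9 to 12 | SAP, read literally |
|---|---|---|
| Relapse | Event on that date (relapse row, read with the *on or prior to* censoring cell) | Censored at the previous negative assessment |
| No relapse | Censored on that date | Censored at the previous negative assessment |

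The second row of this comparison needs no interpretation. The first needs two protocol cells read together.

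**2. How far back the censoring goes.** Disease assessments in Protocol Table 1 fall at Weeks 0, 12, 24 and 52 and then yearly. The gaps are 12, 12, 28 and 52 weeks. Unscheduled efficacy assessments also count (SAP 7.1.2), which can shorten the gap.

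**3. The design figure.** Inputs from SAP 7.6: 90 events, 80% power, two-sided alpha 0.05, 1:1 allocation, medians 8 and 14.5 months, hazard ratio 0.55. Schoenfeld's formula gives events = 4(1.960 + 0.842)² / (ln HR)².
- HR 0.55: 31.4 / 0.357 = 88 events.
- HR 8/14.5 = 0.552: 89 events.
- Power at 90 events and HR 0.55: Φ(√90 × 0.598 / 2 − 1.960) = Φ(0.876) = 80.9%.

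The stated 90 events and 80% power are reproduced.

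**4. Illustrative size.** The documents give no same-day rate. Let q be the share of events that are same-day relapses, assumed to lie between 1% and 10%.
- *Fixed cutoff:* 90(1 − q) events remain, and power follows from the formula above.
- *Trigger counted under the SAP definition:* the 90th event comes later. With 75 patients per arm accrued uniformly over 50 months, exponential RFS and no dropout, expected counted events at month T (up to 50) are (1 − q) × (75/50) × Σ[T − (1 − e^(−λT))/λ]. The sum is over the two arms, with λ = ln 2/8 = 0.0866 for SoC and 0.55 × 0.0866 = 0.0477 for MT-401.
- *One arm only:* the hazard ratio becomes about 0.55/(1 − q) if only SoC is affected, or 0.55(1 − q) if only MT-401 is. This ignores the lost follow-up time, so it overstates the shift.

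| q | Events lost of 90 | Power, fixed cutoff, both arms | Month of 90th event, SAP count, both arms | HR, SoC only | HR, MT-401 only |
|---|---|---|---|---|---|
| 0 | 0 | 80.9% | 44.9 | 0.550 | 0.550 |
| 1% | 0.9 | 80.6% | 45.2 | 0.556 | 0.544 |
| 2% | 1.8 | 80.2% | 45.6 | 0.561 | 0.539 |
| 5% | 4.5 | 78.9% | 46.6 | 0.579 | 0.522 |
| 10% | 9.0 | 76.7% | 48.5 | 0.611 | 0.495 |

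Under the SAP's own event count, a balanced 10% costs 48.5 − 44.9 = 3.6 months and no events. The one-arm columns show only that the direction depends on which arm is affected.

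**The case against.** The strongest reply is that this is an unspecified tie and not two opposing rules. The protocol's *same day* phrase attaches to the disease assessment and not to the start of therapy, so nowhere does the protocol say outright that a relapse found on the day therapy starts is an event. In the SAP, the same *prior to* governs the analysis cutoff. Applied as strictly there, it would drop events dated on the cutoff day, which suggests shorthand. SAP 7.7 could equally be taken to mean that the SAP should be read in line with the protocol tables.

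Part of this stands: the conflict over events is an inference from two cells. The conflict over the censoring date is explicit. The shorthand reading is also weakened by the SAP itself, which writes *on or after* in its DOCR rule and *on or before* in its definition of baseline (7.1.5).

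Three stronger readings are tempting, and the documents do not support them.
- **A loss of power.** A reader might infer that fewer than 90 events would remain. That requires the trigger to be counted under a rule other than the SAP's. SAP 7.4.4 runs the analysis when 90 RFS events have been observed, most naturally as the SAP defines them.
- **Bias against MT-401 through Arm B crossover.** The crossover route puts steps between relapse and treatment: "After relapse and prior to bridging chemotherapy, the patient should perform assessments associated with the Screening visit if not already completed". Protocol 10.2 also requires renewed consent and confirmed eligibility, and crossover depends on an open subgroup and/or sponsor agreement. Therapy given outside that route could start the same day, but nothing indicates that it would do so in one arm only.
- **Loss of relapses confirmed later.** Footnote j to the schedule has "samples stored for central confirmation at later date", so one might read *documented* as the result date. Both documents run RFS to the date of first relapse, and the protocol's word *reported* is no clearer. This is not a difference between the documents.

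**Conclusion.** The mismatch holds. Followed literally, the SAP discards an assessment made on the day new therapy starts, which the protocol tables use, and it does not declare the change. For a same-day relapse this gives an informative censoring where the protocol, read as a whole, gives an event. For a same-day negative assessment it moves the censoring date back.

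The effect is probably small. It touches only patients whose assessment and therapy start share a date, and the documents give no count. The 1% to 10% range above is an assumption. A balanced loss only delays the analysis if the trigger uses the SAP definition. A shift in the hazard ratio needs a difference between arms that the documents do not show, and its direction would be unknown. The planned 90 events, 80% power and hazard ratio of 0.55 are unaffected. The correction is still worth making, because it concerns the primary endpoint and costs almost nothing.

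**What to change.** In SAP 6.4.1.2 and 6.4.1.3, for RFS, DOCR, GRFS, DOR and PFS, replace the *prior to* condition on new anti-cancer therapy with *on or before the date new anti-cancer therapy starts*. Apply it to both the event test and the censoring date, in line with Protocol Tables 9 to 12. If the strict rule is intended, declare and justify it in SAP 7.7.

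A sentence dating relapse by the sample or assessment date would be a useful optional clarification. The protocol tables do not already say this, so it should be labelled as an addition.

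The cost is SAP wording and the matching derivation code. It needs no new data and no change to sample size or power. It should be done before the Group 1 interim analysis.

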assessments	assessment prior to the missed disease	
	assessments	

Abbreviations: AML=acute myeloid leukemia; RFS=relapse-free survival

RFS curves will be estimated using the Kaplan-Meier (KM) product limit method. For Group 1, the hazard ratio and corresponding 95% confidence interval (CI) will be estimated using a Cox proportional hazards model using randomized arm and two stratification factors as covariates. The KM estimate of the medians will be reported, and the corresponding 95% CI will be computed. KM estimates of RFS rates at milestone time points will be reported along with two-sided 95% CIs using Greenwood's formula, provided the minimum follow-up in patients exceeds the time point to support stable estimation of the rate. In addition to the Cox model, a stratified log-rank test will be used to compare the treatment arms, stratified by pre-transplant MRD status (MRD+ vs. MRD-/Unknown) and cytogenetic risk (Unfavorable vs. Other).

RFS is defined as the time between the date of first dose and the date of first relapse per ELN recommendations or death by any cause for Group 2 patients, and will be summarized for Group 2 Subgroup D patients and those in Group 2 who are in CR_{MRD} prior to administration of MT-401.

9.3.3. Primary Efficacy Analysis: Group 2

The primary endpoints for Group 2 are CR rate and duration of complete response. For Group 2 Subgroup C, CR rate is defined as the proportion of treated patients who achieve a best response of CR_{MRD} - or CR using the ELN recommendations. For Group 2 Subgroup D, CR rate is defined as the proportion of treated patients who achieve a best response of CR_{MRD} -. Best overall response (BOR) is defined as the best response designation recorded between the date of first dose and the date of objectively documented progression or relapse per ELN recommendations or the date of subsequent therapy, whichever occurs first. For patients without documented progression or subsequent therapy, all available response designations will contribute to the BOR assessment.

The primary analysis will occur after all patients treated have been followed for 6 months.

For Group 2 Subgroup C, duration of complete response is defined as the time between the date of first documented response of CR_{MRD}- or CR to the date of the first documented relapse per ELN recommendations or death due to any cause, whichever occurs first. For Group 2 Subgroup D, duration of

Confidential Page 53 of 74

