Progressive disease (PD)	Evidence for an increase in bone marrow blast percentage and/or increase of absolute blast counts in the blood: 
 • >50% increase in marrow blasts over baseline (a minimum 15% point increase is required in cases with <30% blasts at baseline; or persistent marrow blast percentage of >70% over at least 3 months; without at least a 100% improvement in ANC to an absolute level ($>0.5 \times 10^9/L$ [$500/\mu L$]), and/or platelet count to $>50 \times 10^9/L$ [$50,000/\mu L$] nontransfused); or • >50% increase in peripheral blasts (WBC X % blasts) to $>25 \times 10^9/L$ ($>25,000/\mu L$) (in the absence of differentiation syndrome); or • New extramedullary disease
Relapse	
Hematologic Relapse (after CR _{MRD-} , CR, CR _i)	Bone marrow blasts $\geq 5\%$; or reappearance of blasts in the blood; or development of extramedullary disease
Molecular relapse (after CR _{MRD-})	If studied pretreatment, reoccurrence of MRD as assessed by RT-qPCR or by MFC

^a The period of stable disease should be at least 3 months to be considered SD.

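### Subgroup C best response: the SAP closes the window at relapse, the protocol at progression or relapse, so a CR recorded after progression counts under the SAP only, and the difference is undeclared

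*SAP*

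**What the plan says.** Both documents build the Subgroup C primary CR rate on best overall response (BOR): the proportion of patients whose best response is CR without MRD, or CR. They differ on when the window for best response closes.

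- **Protocol 9.3.3, first sentence.** BOR is "the best response designation recorded between the date of first dose and the date of objectively documented progression or relapse per ELN recommendations". Subsequent therapy closes the window too, if it comes earlier.
- **SAP 6.4.1.2, first sentence.** The window closes at "the date of objectively documented relapse per ELN recommendations". Here too, subsequent therapy closes it if it comes earlier.
- **Protocol 9.3.3, second sentence.** "For patients without documented progression or subsequent therapy, all available response designations will contribute to the BOR assessment".
- **SAP 6.4.1.2, second sentence.** "For patients without documented relapse or subsequent therapy, all available response designations will contribute to the BOR assessment".

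SAP section 4 undertakes to explain any change from the protocol's methods. SAP 7.7 then states: "There were no changes to the study conduct or planned analyses identified". The protocol's amendment history does not mention the difference.

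**The concern.** Subgroup C patients enter in frank relapse. If the disease worsens without a remission, the ELN category is progressive disease, not relapse. Dropping progression from the rule therefore removes the event that would normally close the window for a non-responder in this subgroup. It is missing from both SAP sentences, so it does not look like a single dropped word.

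At stake is who counts as a responder for a primary endpoint in an open-label, single-arm group. The SAP version can only add responders relative to the protocol. The same BOR rule feeds ORR in Subgroup C, and the SAP carries the Group 2 CR definition over to active-disease patients in Cohorts I-V. The Subgroup C CR rate is also to be read against a retrospective study (protocol 9.3.3) and possibly a synthetic control (SAP 7.4.4), which calls for one settled response rule.

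**Working it through.** **1. The closing events side by side.**

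| | Protocol 9.3.3 | SAP 6.4.1.2 |
|---|---|---|
| Sentence 1: window closes at | progression, relapse or subsequent therapy | relapse or subsequent therapy |
| Sentence 2: all designations count if there is no | progression or subsequent therapy | relapse or subsequent therapy |

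The protocol's own two sentences do not match either: its second names progression but not relapse.

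**2. Does progression count as relapse?** Protocol Table 6 and SAP Table 2 list the two as separate categories. The relapse row begins "Hematologic Relapse (after CR" and covers patients who have had CR without MRD, CR or CRi; molecular relapse requires a prior CR without MRD. Progression in a patient who has reached none of these is not relapse per ELN.

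**3. Who is classified differently?** A Subgroup C patient with, in order:
- no prior CR without MRD, CR or CRi;
- documented progression;
- no subsequent therapy;
- a recorded CR, with or without MRD.

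Under the protocol the window closed at progression, so the patient is a non-responder. Under the SAP it is still open, so the patient is a responder. Subgroup D is not affected in this way. Its patients start in CR with MRD, so worsening that meets the progression criteria also meets the hematologic relapse row.

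**4. Can the case arise?**
- Against: protocol 4.4 ends active follow-up at relapse or progression, and the survival follow-up after it can be by phone (protocol Table 1, footnote e). Protocol 7.1 makes progression a reason for no further MT-401. SAP 7.1 treats MT-401 re-treatment as follow-up anti-cancer therapy, which closes the window.
- For: protocol 7.1 keeps collecting response data as applicable after treatment stops, and SAP 7.1.2 uses all efficacy data from unscheduled visits in deriving endpoints.

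The case is uncommon but not excluded.

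**5. Scale.** No stated figure is disputed. As a check on the plan's own frame, take the 20% row of SAP Table 3 (n = 30, one-sided exact test, alpha 0.05).
- Critical count: the smallest r with P(X ≥ r | 30, 0.20) ≤ 0.05. P(X ≥ 10) = 0.0611 and P(X ≥ 11) = 0.0256, so r = 11.
- Power at 43%: P(X ≥ 11 | 30, 0.43) = 81.1%, against the stated 80%.
- Exact 95% CI at 43%: 25.2% to 62.3%, against the stated 25% to 62%.

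The row reproduces, and the window rule does not alter it.

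Weight of one reclassified patient: 1/30 = 3.3 percentage points. As an illustration, with both the starting count and the number of affected patients assumed:

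| CRs | Rate | Exact 95% CI |
|---|---|---|
| 10/30 (none affected) | 33.3% | 17.3% to 52.8% |
| 11/30 (one affected) | 36.7% | 19.9% to 56.1% |
| 12/30 (two affected) | 40.0% | 22.7% to 59.4% |

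**The case against.** The strongest reply is that the affected group may be empty. Scheduled disease assessment largely stops at progression, and both new therapy and MT-401 re-treatment close the window under either text. That stands, and it limits the size of the point. It does not settle which rule applies if a case occurs.

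A second reply is that protocol 4.1 and SAP 6.1 define relapse more broadly, as marrow blasts of at least 5%, blasts in the blood or extramedullary disease, without requiring a prior remission. This does not rescue the SAP wording. The BOR rule refers to relapse per ELN, which points to the response tables. The broad definition would also class Subgroup C patients as relapsed at entry.

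Three stronger readings are tempting, and the documents do not support them:

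- **That the CR rate is materially inflated.** The plan calls an increase of more than 10-15% over historical CR rates clinically meaningful, and a reader might set 3.3 points beside that. But 3.3 points is the weight of any one patient in 30. Read as percentage points, it would take 3 affected patients to reach 10 (3/30) and 5 to pass 15 (0.15 × 30 = 4.5), and the documents give no expected number.
- **That one patient would tip the test.** Against a 20% historical rate, 10/30 gives a one-sided exact p of 0.061 and 11/30 gives 0.026. That is a chosen example. SAP 7.4.7.5 specifies a two-sided 0.05 test, and doubling gives 2 × 0.0256 = 0.051, which does not cross. Neither document fixes a single historical rate or a two-sided exact convention, and both say the subgroup size rests on no formal power calculation.
- **That PFS would contradict the CR count.** Under either text, a responder who later progresses is both a CR and a PFS event. Only the order of events would be unusual here.

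**Conclusion.** The discrepancy is real and undeclared. The Subgroup C primary CR rate has two definitions, and the SAP's is the more favourable. They part only for a patient with documented progression, no earlier remission and no subsequent therapy who then has a recorded CR. The effect is 3.3 points of CR rate per such patient with 30 in the subgroup. The number of such patients is unknown, probably small and possibly zero. No sample size, power or other stated figure changes.

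This rests on reading relapse per ELN as the relapse rows of the response tables, and on some response data being recorded after progression. It is worth correcting because it decides who is a responder, and because it is better settled before a case has to be classified with results in view.

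**What to change.** 1. SAP 6.4.1.2, first sentence: close the window at documented *progression or relapse* or subsequent therapy, matching protocol 9.3.3.
2. Second sentence of both documents: use *without documented progression, relapse or subsequent therapy*. In the protocol this adds relapse, which that sentence does not now name.
3. List any response recorded after progression separately, outside the primary CR rate.
4. If the SAP rule is what the sponsor intends, declare and justify it in SAP 7.7 and amend the protocol to match.

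The cost is a few words in the SAP, one phrase in the protocol and one listing. No procedure, sample size or power figure changes.
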